3.3.2 Per-Protocol Analysis Set

The per protocol analysis set will include all participants in the ITT population who were hospitalised for at least two consecutive evenings, and who had no protocol deviations (§3.2.3).

3.3.3 Subgroup definitions

A number of baseline characteristics have been identified *a priori* as both predictive of the length of stay and possible sources of treatment effect heterogeneity. These include the variables specified in §5.1

3.4 Allocation concealment and blinding

3.4.1 Allocation concealment

As described, all admitted patients will be randomised prior to arrival at the unit.

3.4.2 Blinded statistician

The analyses will be performed by the trial statistician who will be masked to the lighting conditions experienced by each group for the primary analysis and as far as practically possible for subsequent analyses. This document details the analyses planned *a priori* along with the anticipated assumption checks of the chosen analysis models. These model assumption checks and decisions about the final model will be performed prior to unblinding of the statistician and, if necessary, detailed in an amendment to the SAP that will be published together with the trial results.

4. Presentation of study population

4.1 Screening data, eligibility, recruitment and withdrawal

All participants admitted during the trial period will be randomised. A Consolidated Standards of Reporting Trials (CONSORT) flow diagram will be used to summarise the number of participants as shown in the published protocol. Reasons for withdrawal post-randomisation will be summarised per treatment arm.

4.2 Baseline patient characteristics

As described in the protocol, the following participant demographics and baseline characteristics to be summarised include:

- Demographics: Age, sex, ethnicity, marital status, living situation, years of education, employment status
- Current diagnosis or diagnoses, according to International Classification of Disease 10 (ICD 10) at discharge
- Type of admission (voluntary or involuntary)
- Previous admission history: number of admissions, total number of inpatients bed-days in the 2 years prior
- Details of current presentation based on health records: sleep problems during previous month, level of functioning, alcohol and substance misuse, risk of or actual harm to self or others, current physical health
- Past psychiatric and forensic history, and history of comorbid illnesses

These demographics and baseline characteristics will be tabulated for each treatment arm and overall using descriptive statistics:

- Continuous variables: N, mean and standard deviation, and median and 25th and 75th percentiles as appropriate
- Categorical variables: counts and percentages for categorical variables.

No formal statistical comparisons of baseline characteristics will be conducted.

STATISTICAL ANALYSIS PLAN for BAB-study

5. Analysis

5.1 Analysis of primary outcome

The primary outcome is duration of admission in days in the ITT population. Some patients will be readmitted and re-randomized during the study period. As such, we plan to use a two-level linear mixed-model with duration of stay as dependent variable, with admissions within patient as level 1, and patient as level 2. The primary covariate is group (blue-depleted evening lighting versus normal lighting condition). We will adjust the analyses for a set of pre-specified baseline variables which can be strong predictors of the outcome, as generally recommended by Kahan et al³ and Vittinghoff et al⁴.

These covariates are:

- Age
- Sex
- Diagnosis (categorized as psychotic episodes/disorders, manic episode, severe depressive episode, or none of these)
- Comorbidities (categorized as alcohol/substance use disorders, borderline or other personality disorders, or none of these two)
- Involuntary versus voluntary status at admission
- Number of admissions in the previous 2 years
- Number bed-days in the previous 2 years.

If the model fails to converge using a two-level model we will consider a single-level model.

As this primary outcome is heavily skewed and not normally distributed, we anticipate the use of bootstrapping with the bias-corrected and accelerated (BC_a) method and B=5000 bootstrap samples. If this results in unpractical long computing time, we will use a lower number of bootstrap samples, such as B=1000.

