2.2 Randomization and treatment assignment

A detailed description of the randomisation procedure can be found in the published protocol. Briefly, there will be a 1:1 block randomisation with varying block sizes, using the webCRF program (developed and managed at the Clinical Research Unit Central Norway). Patients who may need admission to the acute psychiatric hospital unit will initially be assessed by other health professionals (general practitioners, out-of-hours emergency services, and other somatic and psychiatric hospital departments). If hospitalisation is deemed necessary, patients will be directed to the acute admissions facility. For the purposes of the trial, patients will be randomised prior to arrival at the unit (i.e. prior to any psychiatric assessment at the acute unit). Clinical considerations may mitigate against following the random allocation procedure, in which cases some participants may be withdrawn immediately from the trial (see section §3.2.2).

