2.3 Determination of sample size

The sample size calculation is described in detail in the published protocol¹.

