3.1 Confidence intervals and p-values

All efficacy and safety estimates will be presented with two-sided 95 % confidence intervals. Accompanying two-sided p-values will be calculated and compared to a 5 % significance level. No adjustments for multiplicity will be made since there is only one primary null hypothesis in this trial. This is in line with “Guideline on multiplicity issues in clinical trials EMA/CHMP/44762/2017”.

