5.2 Analysis of secondary outcomes

Table 1: Overview of secondary outcomes and their planned analyses

Secondary outcomes	Time(s) recorded	Timepoint / timeframe for analysis	Planned analysis	Brief description of recorded data
Clinical assessments and treatment during admission				
Sleep wake cycle parameters	Daily	During admission	Linear	Algorithm estimated variables (from Xenthrum radar sensors)
Clinical Global Impression Scale – Improvement (iCGI-I) - During admission (day-to-day change) - Change from admission	Daily Discharge	During admission At discharge	Linear Linear	Range: -6 (maximum deterioration) to 6 (ideal improvement)
Clinical Global Impression – Severity sub scale (CGI-S)	Baseline and discharge	At discharge	Linear	Likert scale with range: 1 (Normal, not at all ill) to 7 (Among the most extremely ill patients)
Suicide risk	Daily	During admission	Logistic	One item clinical assessment
Need for continuous observation (due to suicide risk)	Daily	During admission	Logistic	One item clinical assessment
Risk of harm to others (Brøset Violence Checklist)	8-hrly	During admission	Linear	6 item scale assessing 6 observable behaviours scored on binary scale. Risk of violence based on total scores: low = 0; moderate = 1-2, higher >2
Staff Observation Aggression Scale-Revised (SOAS-R)	Daily	During admission	Linear	Context and severity of aggressive incidents recorded on scale with range 0 to 100 (0 = not severe, 100 = very severe)
Medication use	Daily	During admission	Logistic/Linear ^a	Daily doses and classes of medication recorded
Change in admission status	Daily	During admission	Logistic ^b	Changes from involuntary to voluntary and vice versa will be recorded
Patient-related experiences and other outcomes				
Adherence (item checklist)	Daily	During admission	Logistic	Duration and reason for exposure to normal lighting; use of blue-blocking glasses on exiting unit and filters on media devices
Satisfaction and benefits	Discharge	At discharge	Linear	10 items scored on 5-point Likert scale (1 = low satisfaction)

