5.2.1 Analysis of continuous secondary outcomes

For continuous variables measured only at discharge (iCGI-I and measure of satisfaction), between group comparisons will be conducted using linear regression adjusting for the same covariates as the in the primary analysis.

The remaining continuous variables are measured two or more times per admission, and these will be analysed using a mixed linear regression model. Where possible, we will use a three-level linear mixed-model with respective secondary outcome as the dependent variable, timepoint (or day of admission) as level 1, admissions within patient as level 2, and patient as level 3. The covariates will include treatment allocation, the prespecified baseline variables and an interaction term between treatment and day of admission. If the model fails to converge, we will consider removing the interaction term and or reduce the number of levels.

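### Baseline CGI-S is collected but is not a covariate in the discharge iCGI-I regression or the length-of-stay model, which costs some precision but causes no bias

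*SAP*

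**What the plan says.** For the primary outcome, SAP Section 5.1 states "we plan to use a two-level linear mixed-model with duration of stay as dependent variable", with admissions nested in patients. On covariates it says "We will adjust the analyses for a set of pre-specified baseline variables which can be strong predictors of the outcome". The list that follows has seven entries: age, sex, diagnosis in four categories, comorbidity in three categories, legal status at admission, and admissions and bed-days over the previous two years. None is a severity rating.

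Table 1 in Section 5.2 gives the recording times of CGI-S, a scale from 1 to 7, as "Baseline and discharge". The same table lists iCGI-I, scored from -6 to 6, and includes change from admission assessed at discharge.

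For outcomes measured only at discharge, iCGI-I among them, Section 5.2.1 says "between group comparisons will be conducted using linear regression adjusting for the same covariates as the in the primary analysis". Baseline CGI-S is therefore absent from that model too. The SAP gives no reason for leaving it out.

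**The concern.** The SAP adjusts in order to use strong predictors of the outcome. Severity on arrival is an obvious candidate, and the trial already records it.

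The case is clearest for discharge iCGI-I. It measures change since admission, so how far a patient can improve plausibly depends on how ill the patient was at the start. The model is a regression on a single measurement, so no repeated measure makes up for the missing starting point.

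For length of stay the argument is the same but weaker. Legal status is binary, diagnosis is a coarse grouping, and prior admissions and bed-days describe history rather than present state. Together they still carry part of the severity information.

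What is at stake is the width of the interval and hence power. Both models are linear and estimate a mean difference between randomised groups, so omitting a baseline predictor does not shift what they estimate.

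**Working it through.** **Inputs from the SAP**
- Test level: "Accompanying two-sided p-values will be calculated and compared to a 5 % significance level" (Section 3.1).
- Allocation: "there will be a 1:1 block randomisation with varying block sizes" (Section 2.2).
- Sample size, power, effect and SD: not in the SAP, since "The sample size calculation is described in detail in the published protocol" (Section 2.3). There is no stated figure to reproduce.

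**Assumed inputs**
- r, the partial correlation of baseline CGI-S with the outcome given the seven listed covariates. The SAP gives none; the range 0.1 to 0.5 is used.
- Starting power of 80% or 90%. A standardised effect of 0.3 was used to set the sample size (175 per arm for 80%, 234 per arm for 90%). The choice of 0.3 is arbitrary and hardly affects the result.
- Clustering of admissions within patients and the planned bootstrap are ignored.

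**Formulas**
- Residual variance is multiplied by 1 - r².
- Interval width is multiplied by √(1 - r²).
- Equivalent gain in sample size is 1/(1 - r²) - 1.
- Power is recomputed for a two-sample comparison of means with the SD replaced by SD × √(1 - r²).

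Example at r = 0.3: 1 - 0.09 = 0.91; √0.91 = 0.954, so the interval is 4.6% narrower; 1/0.91 - 1 = 9.9%.

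| Assumed r | Variance reduction | Interval narrower by | Equivalent extra sample | Power from 80% | Power from 90% |
|---|---|---|---|---|---|
| 0.1 | 1% | 0.5% | 1.0% | 80.5% | 90.3% |
| 0.2 | 4% | 2.0% | 4.2% | 81.7% | 91.2% |
| 0.3 | 9% | 4.6% | 9.9% | 83.7% | 92.5% |
| 0.4 | 16% | 8.3% | 19.0% | 86.5% | 94.3% |
| 0.5 | 25% | 13.4% | 33.3% | 90.0% | 96.3% |

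**Effect of missing baseline ratings**

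If admissions without a baseline CGI-S were dropped, with a share m missing, the variance would change by the factor (1 - r²)/(1 - m). This equals 1 when m = r². The gain would thus be cancelled at 1%, 4%, 9%, 16% or 25% missing for r = 0.1, 0.2, 0.3, 0.4 or 0.5. A complete-case rule would therefore be a poor choice, and the handling of missing values has to be fixed together with the covariate.

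**The case against.** The strongest objection is timing. Section 2.2 places randomisation before the patient arrives and is assessed psychiatrically at the unit, and Section 2.1 calls the trial unblinded. A CGI-S rated by unit staff therefore follows allocation and may be made by someone who knows the ward. Nothing in the SAP shows that it is made before the first evening; Section 2.7 refers to the protocol for the schedule of outcome assessments. This stands: the covariate is acceptable only under a timing condition, and even then rater knowledge remains a residual risk. Its force is limited, because the SAP already adjusts for diagnosis, which Section 4.2 describes as the diagnosis at discharge, after the whole exposure.

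A second objection is completeness. Section 5.1.1 expects almost no missing values in the present covariates, whereas Section 5.2.3 expects many in some secondary outcome variables without saying which. This also stands, and it calls for an explicit rule. Filling with a mean plus an indicator is safe for a covariate fixed before randomisation. That assurance weakens if a post-randomisation rating is missing unequally by arm.

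Third, the size is unknown. At r = 0.1 the gain is negligible, and no document figure rules that out for length of stay.

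A reader might infer more than the SAP supports:
- *That the omission biases the results.* It does not; both models are linear comparisons of randomised groups.
- *That the precision is free.* It is not, given the timing and missing-value conditions.
- *That one covariate list is used for every outcome.* Section 5.3 compares the safety scales with an unadjusted t-test.
- *That the sleep, suicide and violence models need their own baseline items.* Section 4.2 does list "sleep problems during previous month, level of functioning, alcohol and substance misuse, risk of or actual harm to self or others", but the SAP gives these items no scale or degree of completeness, and no gain can be shown.
- *That iCGI-I is the arithmetic difference of two CGI-S ratings.* The SAP does not say so. The matching ranges make dependence on starting severity plausible, not certain.

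**Conclusion.** The point holds as one of efficiency. A severity rating that the trial collects is left out of two linear models, although the SAP's own ground for choosing covariates would favour including it. The case is good for discharge iCGI-I and modest for length of stay.

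The size rests entirely on the assumed partial correlations, and the SAP does not show where in the range of 0.1 to 0.5 either outcome lies. The conclusion that adding CGI-S is harmless rests on two further conditions: the rating precedes the first evening of light exposure, and it is not shaped by knowledge of the ward.

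**What to change.** Settle the following before unblinding, by the amendment route that Section 3.4.2 already provides.

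1. Add baseline CGI-S to the discharge iCGI-I regression. Use only ratings made before the first evening of light exposure, and treat later ratings as missing.
2. State the rule for missing values, for example the overall mean plus a missing indicator, so that no admission is lost. Report the share missing by arm.
3. Add baseline CGI-S to the length-of-stay model on the same conditions. If pre-exposure timing cannot be confirmed, keep the present primary model and pre-specify the version with CGI-S as a sensitivity analysis.
4. If the authors prefer to leave CGI-S out, give the reason in the SAP.

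The cost is a few lines of text, one or two extra parameters per model, and a check of rating times. The downside is that the rating is made after randomisation by possibly unblinded staff and may be missing for some admissions.

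### The BCa bootstrap anticipated because length of stay is heavily skewed tends to exceed the 5% level for a 1:1 difference in mean days; section 5.1 should name one deciding method

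*SAP*

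**What the plan says.** SAP section 5.1 defines the outcome: "The primary outcome is duration of admission in days in the ITT population". The model is a "two-level linear mixed-model with duration of stay as dependent variable, with admissions within patient as level 1, and patient as level 2", with a group effect adjusted for seven baseline covariates. The treatment effect is therefore a difference in mean days on the original scale.

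For inference the section continues: "As this primary outcome is heavily skewed and not normally distributed, we anticipate the use of bootstrapping with the bias-corrected and accelerated (BC_a) method", with B=5000. It adds a fallback: "If this results in unpractical long computing time, we will use a lower number of bootstrap samples, such as B=1000".

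Section 3.1 gives the decision rule: "All efficacy and safety estimates will be presented with two-sided 95 % confidence intervals", and "Accompanying two-sided p-values will be calculated and compared to a 5 % significance level".

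The SAP does not say how a p-value is to be obtained from the BCa bootstrap, or whether patients or admissions are resampled. Section 2.3 leaves the sample size to the protocol, and no SD or shape for length of stay is given. Section 3.4.2 places assumption checks and the choice of final model before unblinding, with any change recorded in a published amendment.

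**The concern.** The reason given for BCa is skewness of the outcome. What matters for a test or an interval is skewness of the estimate. With two arms of similar size and no effect, the skewness of the two arm means cancels in their difference, so there is little for BCa to correct. BCa nevertheless estimates a correction from the sample third moment, and in a long-tailed sample a few very long stays decide it. The arm that holds those stays by chance also has the larger mean, so the correction moves the interval away from zero in exactly those datasets.

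Section 2.4 names a single primary outcome, so this is the trial's only confirmatory test. At stake is that a chance imbalance in a few very long stays could be declared an effect of the lighting.

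**Working it through.** The SAP has no power or error calculation to reproduce. The only stated figure is the nominal 5%.

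**Inputs from the SAP:** two-sided 5% and 95% intervals (3.1); 1:1 allocation (2.2); raw days, the covariates, admissions within patients, BCa with B=5000 (5.1). **Assumed:** number of patients, distribution of stays, intraclass correlation, about 20% extra admissions re-randomised 1:1, and patients as the resampling unit.

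**Step 1: skewness of the estimate.** If both arms have n stays with variance σ² and skewness γ, the skewness of the mean difference is (γσ³/n² − γσ³/n²) / (2σ²/n)^(3/2) = 0.

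**Step 2: what BCa does.** For a mean difference, the estimated acceleration is a = [Σ(x−x̄)³ − Σ(y−ȳ)³] / (6[Σ(x−x̄)² + Σ(y−ȳ)²]^(3/2)). Its true value under no effect is 0, but its sample sign follows the arm with the longest stays. BCa reads the bootstrap distribution at Φ(z0 + (z0+z)/(1−a(z0+z))). With z0 = 0, z/(1−az) ≈ z + az². For z = ±1.96 both limits move the same way, by about 1.96²a = 3.84a. This is a displacement, not a change of width. In a two-arm check (200 per arm, lognormal, log-SD 1.0) the ratio of BCa to Wald width had mean 1.006 and median 1.002.

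**Step 3: size with the planned structure.** Percentage of null trials rejected, using a random-intercept group effect (fixed working intraclass correlation), the SAP's covariates and a patient-level bootstrap:

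| Stays | Sample skewness | BCa, 200 patients (B=1000) | BCa, 400 patients (B=5000) | BCa, 600 patients | BCa, 1000 patients | Wald, 400 patients | Permutation, 400 patients |
|---|---|---|---|---|---|---|---|
| Exponential | 2.1 | 6.4 | 5.6 | 4.9 | 5.8 | 4.9 | 5.0 |
| Lognormal, log-SD 0.8 | 3.3 | 8.1 | 6.7 | 6.3 | not run | 5.0 | 5.1 |
| Lognormal, log-SD 1.0 | 4.5 | 8.5 | 7.8 | 6.9 | 6.9 | 4.8 | 5.1 |
| Lognormal, log-SD 1.2 | 5.9 | 9.9 | 9.0 | 7.1 | 7.2 | 4.8 | 5.3 |
| Lognormal, log-SD 1.5 | 7.9 | 11.6 | 11.0 | 10.3 | 9.3 | 4.2 | 4.9 |

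The 400-patient cells (about 490 admissions) used 10,000 trials. At log-SD 1.0 the Monte Carlo standard error is √(0.078×0.922/10000) = 0.27 points, so the excess of 7.8 − 5.0 = 2.8 points is about ten standard errors. Fitted mixed models with 300 patients gave Wald rejection of 4.0% (log-SD 1.0) and 5.5% (log-SD 1.5), with a standard error of about 1 point.

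**Step 4: other simulations, log-SD 0.8/1.0/1.2.**
- Unadjusted, 2,000 datasets per cell: BCa 7.4/9.1/11.1% at 120 per arm and 5.4/6.6/8.6% at 240 per arm. Wald gave 4–6%.
- Adjusted random-intercept model, about 490 admissions of 350 patients: BCa 7.6/7.9/9.4%, Wald 4.7/4.9/4.7%, permutation 4.3/4.8/5.0%.
- Coverage in that adjusted model with stays 25% shorter in one arm: BCa 92.8/91.6/90.3%, Wald 94.6/94.2/94.0%.

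**Step 5: milder or bounded tails.** Lognormal stays with log-SD 1.0 and 200 per arm gave BCa 8.5%. Capped at an illustrative 30 days, BCa gave 5.8% and Wald 5.2% (standard error about 0.6 points). Other capped cells gave BCa 5–7% and Wald 4–7%. Exponential two-arm cells gave mostly 5–6%, with one at 6.8% where the t-test gave 5.9%.

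**The case against.** The strongest reply is that the size of the problem comes from assumptions. A reader might infer from the table that this trial's error rate is 7–11%. The SAP does not support that: it gives no sample size and no distribution beyond calling the outcome heavily skewed. The excess shrinks with more patients and nearly vanishes with milder or capped tails. That stands, and the figures must stay conditional. Section 2.6 does end open stays 14 days after the last randomisation, but that does not bound the stays of earlier participants.

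Second, BCa is a recognised choice for skewed data, the wording only anticipates it, and section 3.4.2 allows a change before unblinding. This is fair and lowers the severity. But the checks foreseen there concern model assumptions. Seeing skewed residuals would confirm BCa; it would not reveal the displaced interval.

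Three further inferences fail:
- **BCa makes the interval too narrow.** The widths are essentially equal; the interval is displaced.
- **The B=1000 fallback is at fault.** The excess appears at B=5000 as well, and nothing here shows harm from the smaller number.
- **BCa cannot give a p-value, so a model p-value and a BCa interval will clash.** A p-value can be obtained by inverting the interval, and the SAP nowhere commits to that pairing. Were the two paired, the verdicts would have differed in 2.2/3.4/5.1% of datasets at 200 per arm (log-SD 0.8/1.0/1.2). The documented gap is narrower: the source of the p-value and the resampling unit are not stated.

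**Conclusion.** The concern holds in conditional form and is a should-fix. For a 1:1 difference in mean days, the heavy skew given as the reason for BCa is the condition under which BCa exceeds 5%.

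- Lognormal-like stays, log-SD 0.8–1.2, a few hundred patients: about 6–11%, with the lowest cell at 5.4%.
- Exponential or bounded stays: about 5–6% in most cells.
- Full range examined: about 5–12%.
- Mixed-model Wald or permutation test: about 4–6% in nearly all settings.

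These figures assume that significance is read from the BCa interval and that patients are resampled. The direction and mechanism are well supported. The size for this trial cannot be fixed from the SAP.

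**What to change.** By amendment before unblinding, as section 3.4.2 allows, name in section 5.1 one deciding method and take both the p-value and the 95% confidence interval from it. Either option serves:

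1. The adjusted mixed model's own test and confidence interval.
2. A re-randomisation test: permute group labels across the analysed admissions, refit the same adjusted model each time, and obtain the interval by inverting that test. Permuting strictly within blocks is awkward, because the removals in section 3.2.2 leave blocks incomplete.

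Do not combine a permutation p-value with a Wald interval, since the two could again disagree. Keep BCa as a supportive interval, with patients stated as the resampling unit. It could remain the deciding method only if a check on the pooled length-of-stay data, with labels assigned at random, shows that it holds 5%. The B=1000 fallback need not change.

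The cost is SAP wording and modest computing. Rejections become slightly fewer: in one simulated case (stays 25% shorter, 200 per arm) power fell from 66% to 62%. That loss reflects removal of the inflated error.
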